13.1.2 Screen Failures

A patient is considered enrolled in the study when the ICF is signed. Only patients who receive study-assigned procedures will be followed. Patients who provide study consent, but then are determined to be ineligible will be considered screening failures and will not require additional study follow-up. The reason for the screening failure will be clearly documented, the Patient "Enrollment and Visit Log" will be completed and the patient eligibility section in visit 1 as well as a "Study Completion" form will be completed in the eCRF.

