3.0 Protocol Synopsis

Protocol Number	CL00003
Protocol Title	Evaluation of EndoZip™ System (AS) in Obese Patients who failed to reduce weight with non-surgical weight-loss methods
Study Sponsor	
NiTINotes, [name]
 
[contact]
 
[contact]

Sponsor Representative	
[name] VP QA, Regulatory and Medical Affairs

Study Type	Pilot study
Study Product	EndoZip™ System (AS)
Study Location	Europe, Israel
Study Centers	
 1. Hospital Universitario HM Sanchinarro, Madrid, SPAIN 2. Fondazione Policlinico Universitario Agostino Gemelli IRCCS (CERTT), Rome, Italy 3. Rabin Medical Center, Petah Tikva, Israel

	
Title: Evaluation of EndoZip™ System (AS) in Obese Patients who failed to reduce weight with non-surgical weight-loss methods
	
Document No: CL00003	Rev: 1.0	Page: 9 of 83

Investigators	
 1. [name] 2. [name] 3. [name]
Study Duration	The duration for each participant will be 12 months; the total study duration is expected to be approx. 18 months
Study Design	The study is planned as a multicenter, prospective, single-arm, open-label, controlled clinical trial.
Planned Visits	
 • Office visits: 1 week, and 1, 2, 4, 6, 8, 10, and 12 month(s) • Remote follow up (by Phone): 3, 5, 7, 9, and 11 month(s) • Endoscopy follow up: 2 and 6 months • Motility evaluation by Gastric Emptying Breath Test (GEBT): 6 months • Physical examination, vital signs, waist circumference and BMI: 1 week, 1, 2, 4, 6, 8, 10 and 12 months • Blood tests: 2, 6 and 12 months • IWQOL-Lite: 2, 6 and 12 months • Sleep Apnea (only for the relevant population): 2, 6 and 12 months
Patient Population	Male and Female with obesity, BMI of 30-40 kg/m ² , between the ages of 21 and 70 who failed to reduce weight with non-surgical weight-loss methods
Planned # of Patients	Up to 45 patients
Planned # of Sites	Up to 5 clinical sites
Planned # of Patients per Site	Up to 20

	Title: Evaluation of EndoZip™ System (AS) in Obese Patients who failed to reduce weight with non-surgical weight-loss methods	
Document No: CL00003	Rev: 1.0	Page: 10 of 83

Study Objective	
The objective of this study is to evaluate the safety and effectiveness of the EndoZip system procedure, coupled with lifestyle modifications, for weight reduction in obese patients with BMI of 30-40 kg/m².

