10.0 Study Design

[figure not shown]
This multicenter, prospective, single arm study will include up to 45 patients (10-20 patients per site), aimed at evaluating the performance of the EndoZip System in obese patients who failed to reduce weight with non-surgical weight-loss methods.

The first two (2) patients in each site will be considered as run-in period, to compensate for any learning curve that may be required for the EndoZip performance evaluation.

Patients will be enrolled at up to 5 clinical sites in Europe and Israel. Patients who meet the eligibility criteria is expected to come the clinic for at least 10 visits.

	
Title: Evaluation of EndoZip™ System (AS) in Obese Patients who failed to reduce weight with non-surgical weight-loss methods
	
Document No: CL00003	Rev: 1.0	Page: 33 of 83

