10.1 Study Flow Chart

11.0 Patient Selection and Enrollment

After being informed of the nature of the study, the patient will sign a written informed consent form (ICF) that has been approved by the appropriate Institutional Ethics Committee (IEC) and regional Competent Authority (CA). Enrollment of up to 45 patients is planned.

Patients will be considered for the study if they meet the specific inclusion/exclusion criteria. The criteria for enrollment must be followed explicitly.

	Title: Evaluation of EndoZip™ System (AS) in Obese Patients who failed to reduce weight with non-surgical weight-loss methods		
Document No: CL00003	Rev: 1.0	Page:	34 of 83

Enrollment completion is expected to take place up to 6 months following IEC approval of the study.

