14.0 Statistical Analysis

14.1 Sample Size Determination

This is a pilot study that will include up to 45 patients; no statistical considerations were made to determine the sample size.

The first two (2) patients per site will be considered as run-in period, to compensate for any learning curve that may be required for the EndoZip performance evaluation.

Safety evaluation will include all enrolled patients.

	Title: Evaluation of EndoZip™ System (AS) in Obese Patients who failed to reduce weight with non-surgical weight-loss methods		
Document No: CL00003	Rev: 1.0	Page:	53 of 83

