14.2 Description of statistical methods

14.2.1 Analysis of Populations

Full Analysis Set (FA): includes all enrolled patients who undergone EndoZip procedure, excluding patients who enrolled in the run-in period.

Modified Full Analysis Set (mFA): The modified full (mFA) analysis set will include all patients who have at least one post initiation follow up visit and met the study Eligibility Criteria, and enrolled after the run-in period.

Per-Protocol (PP) analysis set: includes all patients from the mFA set who do not have any major protocol violations, and enrolled after the run-in period, and enrolled after the run-in period.

Statistical Analysis of Analysis Sets: Safety assessments will be performed on all enrolled patients set.

The mFA will serve as the principal data analysis set for the primary and secondary statistical efficacy endpoints. The primary, secondary efficacy assessment will also be performed on the PP and FA cohorts for descriptive purposes and to show consistency of study results.

14.2.2 General Methods:

Statistical analyses will be mainly descriptive in nature. Any statistical tests if performed will be two-sided, unless otherwise stated.

Study data will be summarized with descriptive statistics and presented in tables and figures. Continuous variables will be summarized by a mean, standard deviation, minimum, median and maximum and categorical variables by a count and percentage. If multiple measurements are taken in a single patient, statistics described below will be appropriately modified to accommodate the within patient correlation.

Any deviation from specified statistical plan will be in addition to “per protocol” analysis and will be reported as such Post-hoc analysis will be conducted according to the existing data gathered, if necessary.

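### Section 14 puts safety on all consented patients and the synopsis puts it on treated patients without the run-in; neither is the set of all treated patients

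*Combined protocol and SAP*

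**What the plan says.** **Enrolment.** Section 13.1.2: "A patient is considered enrolled in the study when the ICF is signed". It continues: "Patients who provide study consent, but then are determined to be ineligible will be considered screening failures and will not require additional study follow-up". Consent comes before testing. Laboratory work, the PHQ-9 and the breath test belong to Visit 1 (Section 13.1). The pregnancy test, ECG and screening endoscopy follow on the procedure day (Section 13.3).

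**Safety set.** Section 14.2.1: "Safety assessments will be performed on all enrolled patients set". Section 14.1 says the same. The synopsis (Section 3.0, Analysis Populations) instead names the Full Analysis (FA) set: patients who underwent the procedure, with run-in patients removed.

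**Run-in.** Section 10.0: "The first two (2) patients in each site will be considered as run-in period". Section 14.1 gives the purpose: "to compensate for any learning curve that may be required for the EndoZip performance evaluation". The set definitions in the synopsis and Section 14.2.1 speak of patients enrolled in, or after, the run-in.

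**Ceiling.** Section 11.0: "Enrollment of up to 45 patients is planned". Of this number Section 14.1 says "no statistical considerations were made to determine the sample size".

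**Event recording.** Section 15.1 starts adverse event collection at enrolment. Section 14.3 sends events between consent and procedure to medical history, unless they are serious and caused by a procedure the protocol requires.

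**The concern.** Section 8.1 makes safety part of the primary objective, and Section 14.5 reports it as cumulative incidence. The denominator therefore matters, and the documents give two.

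Under Section 14, the denominator includes everyone who signed consent. Several exclusions in Section 11.2 (lipids, INR, HbA1c, PHQ-9) can be met only after signature, so untreated but enrolled patients are an expected result of the design. They cannot have a device event, they are not followed, and most of their pre-procedure events go to medical history. They add to the denominator and almost nothing to the numerator, so every rate is pulled down.

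Under the synopsis, the denominator contains only treated patients, but the first procedures at each site are dropped from the safety results. Those are the procedures for which the plan itself allows a learning curve.

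If this is left open, the denominator can be chosen after the events are known.

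**Working it through.** There is no sample-size calculation to reproduce, because Section 14.1 disclaims one. The check is a count under each definition.

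**Inputs from the documents:** ceiling 45 (Sections 11.0 and 14.1); two run-in patients per site (Section 10.0); three named sites, with a maximum given as "Up to 5 clinical sites" (synopsis).

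**Assumed input:** *s*, the share of consented patients never treated. The documents give no value, so 10-40% is shown.

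**1. Section 14 set, all consented.** Suppose 45 consent and events arise only in treated patients.
- Treated = 45 × (1 − *s*).
- Reported rate = true rate among treated × (1 − *s*).
- Upper two-sided 95% Clopper-Pearson limit with zero events = 1 − 0.025^(1/n).

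| *s* | Treated | True 10% reported as | 3 patients with an event: of 45 / of treated | Zero-event upper limit: n = 45 / n = treated |
|---|---|---|---|---|
| 10% | 40.5 | 9% | 6.7% / 7.5% | 7.9% / 8.8% |
| 20% | 36 | 8% | 6.7% / 8.3% | 7.9% / 9.7% |
| 30% | 31.5 | 7% | 6.7% / 9.7% | 7.9% / 11.2% |
| 40% | 27 | 6% | 6.7% / 11.1% | 7.9% / 12.8% |

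The last two columns use 40 and 31 treated where the expected count is fractional. At *s* = 20%, three affected patients are 6.7% of 45 (95% CI 1.4-18.3%) and 8.3% of 36 (1.8-22.5%).

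**2. Synopsis set, FA.** Treated patients omitted = 2 × sites, if every run-in place goes to a treated patient.
- Three sites: 2 × 3 = 6, leaving 45 − 6 = 39 if 45 are treated (6/45 = 13% omitted).
- Five sites: 2 × 5 = 10, leaving 45 − 10 = 35 (10/45 = 22% omitted).

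**3. What the ceiling counts.** Treating 45 would need 45 / (1 − *s*) consents: 50, 57, 65 or 75 at *s* = 10, 20, 30 or 40%, rounded up.

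**4. What the run-in counts.** The rule names neither consent order nor treatment order. Three texts bear on it:
- The learning-curve purpose points to treated patients.
- Section 14.2.1 ties the effectiveness sets to enrolment after the run-in, which under Section 13.1.2 means consent order.
- Section 13.1 assigns identifiers in sequence at consent and does not reuse them.

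The rule is therefore open.

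**The case against.** **Enrolled is used loosely and will be read as treated.** There is support for this. Section 11.0 speaks of eligibility criteria for enrolment, and the interim analysis in Section 14.7 counts enrolled patients with two months of follow-up, which only treated patients can have. But Section 13.1.2 holds the only explicit definition, and it says consent. What stands is that usage is inconsistent, which is itself a reason to fix the wording.

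**The rates can be recomputed.** Section 14.5 requires a full listing of adverse events, so the counts are not lost. That stands. The planned headline rates would still be the diluted ones.

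**This is a mainly descriptive pilot.** True, and no hypothesis test on safety is affected. That limits the consequence to how the rates are reported.

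**Stronger readings that a reader might infer.**
- *That the run-in counts untreated patients and so fails.* The text does not establish this: it says only the first two patients, and the purpose points to treated ones. Even under consent order, with independent failures, the chance that a site loses both places is *s*² (1-16% for *s* = 10-40%). The chance of losing at least one is 1 − (1 − *s*)² (19-64%).
- *That the trial will fall short of 45 treated patients.* The 45 is a ceiling with no statistical basis, so no target is missed.
- *That enrolment should be redefined as the start of the procedure.* With Section 15.1 as worded, this would end event collection between consent and procedure and could hide harm from the screening endoscopy.

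**Conclusion.** The point holds for the safety set. Section 14, read with the enrolment definition, adds untreated and unfollowed patients to the denominator. The synopsis removes 6 to 10 treated ones, at three to five sites. The two conflict, and neither describes all treated patients.

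The size of the dilution depends on a screen-failure rate that the documents do not give. If 10-40% of those consented are never treated and events arise only in treated patients, a true 10% rate reads as 9% down to 6%. The effect of dropping the run-in patients cannot be sized, because nothing in the documents says how their event rate would differ.

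The run-in rule and the ceiling are undefined as to which patients they count. That needs a sentence each; the documents do not show that either rule goes wrong. The correction is cheap, concerns a primary-objective result, and should be made before safety data are reviewed.

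**What to change.** 1. In the synopsis and Sections 14.1 and 14.2.1, define one safety set: all patients in whom the EndoZip procedure was started, run-in included. Use it as the denominator for all event rates in Section 14.5. *Started* is safer than *underwent*, because Section 7.2 lists a failed procedure among the anticipated risks.
2. Keep the consent-based definition in Section 13.1.2 and adverse event collection from that point in Section 15.1. Align Section 14.3 with it.
3. List separately any events in consented but untreated patients, including serious events due to procedures the protocol requires, such as the screening endoscopy.
4. In Sections 10.0 and 14.1, state that the run-in patients are the first two treated at each site. Change the set definitions in the synopsis and Section 14.2.1 to match.
5. In Section 11.0 and the synopsis, say whether the ceiling of 45 counts consented or treated patients.

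Cost: wording only. Reported event rates become slightly less favourable than under the all-consented denominator, and more than 45 consents may be needed if the ceiling counts treated patients.

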13.2 Randomization

NA –Single study arm

13.3 Visit 2 - EndoZip Procedure Day

The patients will undergo the EndoZip procedure within 30 days after signing the Informed Consent Form (ICF).

	Title: Evaluation of EndoZip™ System (AS) in Obese Patients who failed to reduce weight with non-surgical weight-loss methods		
Document No: CL00003	Rev: 1.0	Page:	43 of 83

Pre-Examination Procedures:

- Verify the informed consent was obtained after explaining all risks, benefits, and alternatives to the candidate.
- Verify all Laboratory results were documented.
- Verify the GEBT results were documented.
- Verify the Quality of life (IWQOL) and Psychological health (PHQ-9) questionnaires were documented.
- For patients who suffer from Sleep Apnea, verify the Sleep Apnea test results were documented.
- Verify the patient eligibility.
- Verify all background/clinical information, demographic and medical history was documented.

In addition the patients will undergo / repeat the following test prior the EndoZip procedure:

- Physical examination
- Vital signs (blood pressure and heart rate - supine, pulse, body temperature, respiratory rate (RR) and SpO2) will be measured. *Note: if blood pressure measurement > 160/100 it is recommended not to perform the EndoZip procedure.*
- Weight, Height, Waist circumference will be measured.
- ECG test
- Female patients, pregnancy test
- Endoscopy screening procedure to R/O any findings in the upper GI tract.

EndoZip Procedure

The EndoZip procedure will be performed by the clinical investigator(s), experienced in endoscopic suturing devices according to local standard of care. Physicians in training (residents, fellows) and physician assistants may assist the Study Investigator in any aspect of this part of the procedure as per standard procedures and practices at his/her institution. Anesthesia will be applied as well per the standard of care. In order to ensure correct operation of the EndoZip System a NiTiNotes representative may attend the procedure. Using the EndoZip system, will followed by specific training with the device that will be provided by the sponsor prior to the study. EndoZip System operation is described in the Instruction for Use.

Once the procedure is completed, relevant data will be documented in the Electronic Case Report Form (eCRF) in addition, findings, diagnosis as well as physician's usability and satisfaction questionnaire will be recorded/completed.

	Title: Evaluation of EndoZip™ System (AS) in Obese Patients who failed to reduce weight with non-surgical weight-loss methods		
Document No: CL00003	Rev: 1.0	Page:	44 of 83

The EndoZip procedure will be recorded on digital media via the endoscope equipment used during the procedure. Only the patient study ID and initials should appear in the recorded video.

All endoscopy still pictures will be saved in a digital format. Quality copies of the pictures taken during endoscopy will be provided to the sponsor.

These videos and pictures will be archived and may be used in future analyses to, for example, provide further information about observed sutures applied during the EndoZip procedure.

Any AE will be documented in the eCRF.

Post-Examination

Patients will be transferred to recovery room for observation per standard endoscopic suturing standard of care.

Standard post endoscopic suturing care is required to achieve optimal results. The study post-procedural guidance including diet protocol and physical activities is provided in Appendix A. Lifestyle modification will be provided by a dietitians/nutritionists.

Follow-up call will be conducted 1-2 working days after patients' discharge to verify that there has been no change in patients well-being. Any AE will be documented in the eCRF.

13.4 Visit 3 – Follow Up 1 Week Post Procedure (7-10 days after patient discharge)

The following activities will be performed and documented at this visit:

- Physical examination
- Vital signs (blood pressure and heart rate - supine, pulse, body temperature, respiratory rate (RR) and SpO2) will be measured
- Weight, Height, Waist circumference will be measured.
- Patients will meet with dietitians/nutritionists where he/she will be queried regarding their adherence to the post-procedure diet protocol and reminded to follow the instructions.
- Any adverse event experienced by patient since last visit will be recorded.

The relevant data will be documented in the eCRF.

13.5 Visit 4 – Follow Up 1-month Post Procedure

This visit will be conducted 1 month (\pm 1 week) after the procedure.

	
Title: Evaluation of EndoZip™ System (AS) in Obese Patients who failed to reduce weight with non-surgical weight-loss methods
		
Document No: CL00003	Rev: 1.0	Page:	45 of 83

The following activities will be performed and documented at this visit:

- Physical examination
- Vital signs (blood pressure and heart rate - supine, pulse, body temperature, respiratory rate (RR) and SpO2) will be measured
- Weight, Height, Waist circumference will be measured.
- Patients will meet with dietitians/nutritionists where he/she will be queried regarding their adherence to the post-procedure diet protocol and reminded to follow the instructions.
- Concomitant medication will be recorded including any changed from the last visit.
- Any adverse event experienced by patient since last visit will be recorded.

The relevant data will be documented in the eCRF.

13.6 Visit 5 – Follow Up 2 months Post Procedure

This visit will be conducted 2 months (± 1 week) after the procedure.

The following activities will be performed and documented at this visit:

- Physical examination
- Vital signs (blood pressure and heart rate - supine, pulse, body temperature, respiratory rate (RR) and SpO2) will be measured
- Weight, Height, Waist circumference will be measured.
- Laboratory evaluations – Hematology, - CBC with differential, Comprehensive Metabolic Panel Kidney and liver functions – blood glucose, HbA1c, Urinalysis, lipid profile.
- Endoscopy procedure to inspect the stomach stitches.
- Patients will require to fill-out the IWQOL questionnaire
- Patients will meet with dietitians/nutritionists where he/she will be queried regarding their adherence to the post-procedure diet protocol and reminded to follow the instructions.
- Concomitant medication will be recorded including any changed from the last visit.
- Any adverse event experienced by patient since last visit will be recorded.
- Patients with diagnosed Sleep Apnea disorder will undergo HSAT (home sleep apnea testing).

The relevant data will be documented in the eCRF.

13.7 Visit 6 – Follow Up 6 months Post Procedure

This visit will be conducted 6 months (± 1 week) after the procedure.

	Title: Evaluation of EndoZip™ System (AS) in Obese Patients who failed to reduce weight with non-surgical weight-loss methods		
Document No: CL00003	Rev: 1.0	Page:	46 of 83

The following activities will be performed and documented at this visit:

- Physical examination
- Vital signs (blood pressure and heart rate - supine, pulse, body temperature, respiratory rate (RR) and SpO₂) will be measured
- Weight, Height, Waist circumference will be measured.
- Laboratory evaluations – Hematology, - CBC with differential, Comprehensive Metabolic Panel Kidney and liver functions – blood glucose, HbA1c, Urinalysis, lipid profile.
- Endoscopy procedure to inspect the stomach stitches.
- Patients will require to fill-out the IWQOL questionnaire
- Patients will meet with dietitians/nutritionists where he/she will be queried regarding their adherence to the post-procedure diet protocol and reminded to follow the instructions.
- Gastric Emptying Breath Test (GEBT)
- Concomitant medication will be recorded including any changed from the last visit.
- Any adverse event experienced by patient since last visit will be recorded.
- Patients with diagnosed Sleep Apnea disorder will undergo HSAT (home sleep apnea testing).

The relevant data will be documented in the eCRF.

13.8 Visit 7 – Follow Up 12 months Post Procedure

This visit will be conducted 12 months (± 1 week) after the procedure.

The following activities will be performed and documented at this visit:

- Physical examination
- Vital signs (blood pressure and heart rate - supine, pulse, body temperature, respiratory rate (RR) and SpO₂) will be measured
- Weight, Height, Waist circumference will be measured.
- Laboratory evaluations – Hematology, - CBC with differential, Comprehensive Metabolic Panel Kidney and liver functions – blood glucose, HbA1c, Urinalysis, TSH, lipid profile.
- Patients with diagnosed Sleep Apnea disorder will undergo HSAT (home sleep apnea testing).
- Patients will require to fill-out the IWQOL questionnaire
- Patients will meet with dietitians/nutritionists where he/she will be queried regarding their adherence to the post-procedure diet protocol and reminded to follow the instructions.
- Concomitant medication will be recorded including any changed from the last visit.
- Any adverse event experienced by patient since last visit will be recorded.

	
Title: Evaluation of EndoZip™ System (AS) in Obese Patients who failed to reduce weight with non-surgical weight-loss methods
		
Document No: CL00003	Rev: 1.0	Page:	47 of 83

The relevant data will be documented in the eCRF.

